13.0 SELECTION CRITERIA FOR INVESTIGATORS/SITES

- The Investigator/s selected to participate in this study is/are qualified Orthopaedic surgeon/s.
- Research assistants and study staff will be representatives of the Institute under the direction of the Principal Investigator.
- Any conflicts of interest (including financial assistance from other parties) will be declared by Investigators and research personnel before the commencement of the trial.
- Investigators must maintain a list of any delegated duties with respect to the trial, and the persons and qualifications of those persons to whom the duties are assigned.
- Sites must be able to demonstrate that adequate subject recruitment is likely to be possible, with necessary time available to conduct the study to GCP requirements, and with adequate facilities and trial staff.
- Investigators must provide medical care to a trial participant that is necessary
 as a result of any adverse event experienced during or following the trial that is
 deemed related to the trial.
- Investigators must possess, prior to trial commencement, a favorable Ethics Committee endorsement of trial protocol, Patient Information and Consent forms and any other information given to subjects.

 All trial related documents are subject to Ethics Committee review. A regular trial report is also mandatory for provision to the Ethics Committee (in accordance with local requirements).

- The Investigator/Institution shall permit trial related monitoring, audits, Ethics review and regulatory inspections, by providing direct access to source data/documents and any other trial related documentation.
- The trial MUST be conducted according to the approved protocol.
- Any deviation from the protocol must be documented for later review.
- No deviation from protocol may occur without Ethics Committee endorsement,
 unless it is required to prevent imminent harm to participants
- Investigators must ensure subjects have given informed, written consent, with all trial procedures and risks adequately explained.

14.0 ADMITTANCE OF PATIENT

The Investigator must wait for written Ethics Committee and Governance approval prior to beginning the study or enrolling participants.

A review of the inclusion and exclusion criteria must be completed by the Investigator pre-operatively for each patient.

A patient will be identified as a patient in this clinical trial upon signing a Patient Information Sheet and Consent form.

15.0 PATIENT ACCOUNTING

The Investigator or designee will complete an informed consent log with details (patient number and initials) of any patient signing a consent form to participate in this study.

Clinical trial data will be monitored regularly to identify any trends and adverse events. Documentation of participants who voluntarily withdraw from the study or who are lost to follow-up will be obtained on a Study Completion Form.

16.0 QUALITY ASSURANCE OF DATA

Case Report Forms (CRFs) will be routinely reviewed by the Principal Investigator for completeness and accuracy as well as any evidence which may be indicative of patient risk. When any discrepancies are noted, they will be resolved with the Investigator and/or individual designated by the Investigator. When the data are incomplete, attempts will be made to obtain the data whenever possible.

Clinical Research staff from Stryker Australia will monitor the investigational site at regular intervals to ensure compliance with the protocol and capture of any data or complications not already documented. Verification of the data from source documents will also be conducted by the Stryker monitors.

17.0 MANAGEMENT OF CONCURRENT EVENTS

17.1 Concurrent illness/procedures

Participants requiring concurrent procedures or medications for inter-current illnesses or adverse events will not be restricted throughout the study. Given the typical patient population receiving total knee joint replacements, it can reasonably be expected that concurrent illnesses or procedures may be experienced by study participants.

17.2 Withdrawal from Study

Participants will be advised that they may voluntarily withdraw from the study at any time, for any reason and they are not obligated to reveal the reason to the Investigator and it will not affect their medical care. However, in such cases, appropriate effort will be made to determine the reason for withdrawal from the study. The Investigator may request a letter from the patient noting his or her desire to withdraw from the study. All attempts to locate participants lost to follow up will also be documented.

Participants will be informed that should they withdraw from the study they should remain under the care of an appropriately experienced physician until the physician deems further follow-up unnecessary.

The following are circumstances for which a patient would be identified as not continuing their participation in the study:

- Study Completed / Terminated
- Death
- Unable to Return
- Unwilling to Return
- Concurrent Illness
- Lost to follow-up
- Re-operation of the affected knee joint, including revision of total knee replacement components
- Other

Additionally, the patient may be withdrawn by the Investigator, if he/she is unable to continue participation in the study due to some condition unrelated to this study.

A Study Completion Form will be completed for all participants who withdraw from the study.

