7.0 STUDY DESIGN

This study will be conducted as a randomised controlled trial, designed to limit confounding bias. Participants will be recruited and assessed against the Inclusion and Exclusion criteria. If participants met these criteria they will be randomised to either the Control Group or the Intervention Group, with no other factors of influence.

This will be achieved via a block randomisation process. A central randomisation list will be computer generated by a consultant statistician. Once a patient has met criteria for enrolment, the Principal Investigator or designee will phone/email the Sponsor with the Initials, Date of Birth and Patient Number (assigned in ascending order at time of recruitment). A randomisation number, corresponding to a randomisation envelope held at the study site, will be provided. Once this number is received the envelope will be located and opened. The Principal Investigator will note the group allocation in the Case Report Form.

Patients will be blinded to their group allocation. This will allow minimal bias when completing post-operative questionnaires.

Pre- and post-operative x-rays will also be reviewed by a blinded reviewer.

Control Group - Neutral Mechanical Alignment using Navigation

Participants randomised to the Control Group will undergo Total Knee Replacement (TKR) with the goal of neutral alignment to the mechanical axis. This is the standard method for TKR with Triathlon[®] Knee System and this group will serve as a control reference for the intervention group.

Intervention Group - Kinematic Alignment using ShapeMatch®

Participants randomised to the Intervention Group will undergo TKR with the goal of kinematic alignment, re-aligning the limb to its pre-disease kinetic alignment.

Both groups will undergo treatment in parallel. The study will be conducted as a two-centre study with approximately 7 surgeons performing surgery for this study.

Patients will be followed up until 12 months post-surgery and those participating in the extension study will be followed until 5 years post-surgery.

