Oxford Knee Score: A patient-completed 12-item questionnaire, designed specifically for patients undergoing total knee replacement. Each of the 12 items has 5 scoring categories. It is short, practical, reliable, valid and sensitive to clinically important changes over time (Dawson et al, 1998).

The International Knee Society System (IKSS): a universally-accepted tool for assessment of TKR clinical and functional outcomes. It separates findings in the operated knee with findings in the patient's function. As such the Knee Score is not artificially affected by co-morbid conditions. The Knee Score consists of points given for pain, range of motion, and stability in both the coronal and sagittal planes, with deductions for fixed deformity, and extensor lag. The Function Score consists of points given for the ability to walk on level surfaces, and the ability to ascend and descend stairs, with deductions for the use of external supporting devices (Insall et al., 1990).

FJS-12: The Forgotten Joint Score is a newly-developed twelve-item, self-reported assessment of how aware recipients of hip and knee joint replacement are of their joint in everyday life (Behrend et al., 2010).

WOMAC: The Western Ontario and McMaster Universities Arthritis Index is a set of standardised self-administered questionnaires used to evaluate the condition of patients with osteoarthritis of the hip and knee. It assesses the pain, joint stiffness, physical, social and emotional function of a person with osteoarthritis. A reduced version of WOMAC has been validated and published by Whitehouse et al (2003) and will be used in this study.

Euro-Qol (EQ-5D-3L): The EQ-5D-3L is a standardised patient-completed instrument for use as a measure of health outcome (Fransen and Edmonds, 1999). It consists of dimensions: mobility, self-care, usual activities, pain/discomfort, and

anxiety/depression. There are 3 levels of severity to select from within each dimension.

VAS Pain: A graphic Visual Analogue Scale (VAS) used as measurement instrument for patients to indicate their level of pain. The amount of pain that a patient feels is believed to range across a continuum from none to an extreme amount of pain i.e. from the patient's perspective this spectrum appears continuous - their pain does not take discrete jumps, as a categorization of none, mild, moderate and severe (Wewers et al., 1990).

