12.0 STATISTICAL METHODS

12.1 Sample Size Justification

The New Zealand National Joint Registry reported a mean Oxford Knee Score of 37.05 (with a standard deviation of 8.30) at 6 months following total knee arthroplasty, using mostly conventional instruments (NZOA New Zealand Joint Registry, 2010). The registry also reports the following scoring categories: Excellent >41, Good 34-41, Fair 27-33, and Poor <27.

Kamat et al. (2009) undertook a study comparing the clinical outcomes of manual versus computer-assisted surgery instrumentations systems. A 5-point change in Oxford Knee Scores at a post-operative period of 6 months was determined to be a clinically meaningful difference.

A minimum of 45 patients per group are required, based on an improvement from 37 (mean Oxford Knee Score reported in the New Zealand registry) to 42 (scoring category of excellent), with 80% power and significance level of 5%.

An additional 5 patients per group (10%) has been included into the target patient number to allow for loss to follow-up, bringing the target to 50 patients per group.

A maximum of 100 patients will be enrolled in the Extension Study.

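### Section 17.2 does not separate stopping clinic visits from withdrawing consent to outcome collection, so some obtainable 12-month Oxford Knee Scores may be lost

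*Combined protocol and SAP*

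**What the plan says.** Section 17.2 gives a list of circumstances in which a patient counts as no longer participating. Among them are Concurrent Illness, Unable to Return and Unwilling to Return. It then adds a separate route: "the patient may be withdrawn by the Investigator, if he/she is unable to continue participation in the study due to some condition unrelated" to the study. A Study Completion Form follows for everyone who withdraws. No criteria are given for when illness or difficulty attending should end follow-up, and the section says nothing about collecting outcomes afterwards.

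Section 17.1 says of this population that "it can reasonably be expected that concurrent illnesses or procedures may be experienced by study participants".

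The primary outcome is the Oxford Knee Score at 12 months (section 3.0). Section 11.0 describes the instrument as "A patient-completed 12-item questionnaire, designed specifically for patients undergoing total knee replacement". The same section has forms completed at the time of each required visit, and the visit-window text in section 1.0 classes a patient not seen in the window (12 months, plus or minus 2 months) as having missed that visit.

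On knowledge of the arm, section 7.0 says "The Principal Investigator will note the group allocation in the Case Report Form". It describes only the patients and the x-ray reviewer as blinded.

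Sections 16.0 and 21.2 say in general terms that incomplete data will be obtained where possible. Section 12.2 names neither an analysis population nor a missing-data method.

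**The concern.** The treatment is one operation. Once it has been done, a patient who becomes ill, cannot travel or does not want to attend clinic can in many cases still answer a 12-item questionnaire. The plan has one category, not continuing, for both the patient who will not come to clinic and the patient who refuses any further data collection. Staff who follow section 17.2 have no instruction to seek a 12-month score from the first kind of patient.

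Two things are at stake. The first is precision: section 12.1 allows 5 losses per arm, and some of that allowance may go on patients whose primary outcome was obtainable. The second is bias: exits for illness or inability to attend are plausibly related to function, and one route depends on a judgement by an Investigator who probably knows the allocation. If such exits differ between arms, a comparison of the patients who remain is no longer fully protected by randomisation.

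This point covers the main 12-month trial and patients with neither re-operation nor un-blinding. Those exits (sections 17.2 and 17.3) are a separate matter.

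**Working it through.** **1. Reproduce the planned size.** Inputs from section 12.1:
- a difference of 5 points (37 to 42);
- "a mean Oxford Knee Score of 37.05 (with a standard deviation of 8.30) at 6 months following total knee arthroplasty", so SD = 8.30;
- 80% power and 5% significance. Sidedness is not stated and two-sided is assumed; a one-sided test gives 35 per arm and does not reproduce the plan.

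Normal approximation: n per arm = 2 × [SD × (1.960 + 0.842) / 5]² = 2 × (8.30 × 2.802 / 5)² = 43.3, rounded up to 44. The two-sample t-test version gives 44.2, rounded up to 45. This matches "A minimum of 45 patients per group are required". With 10% loss, 45 / 0.90 = 50. The sample size is not in error.

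**2. Power by number analysed.** Two-sample t-test with standardised difference 5 / 8.30 = 0.602, non-centrality 0.602 × √(n/2), and 2n − 2 degrees of freedom:

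| Analysed per arm | Lost of 50 | Non-centrality | Power |
|---|---|---|---|
| 50 | 0 | 3.01 | 84.7% |
| 45 | 5 (planned) | 2.86 | 80.7% |
| 40 | 10 (assumed) | 2.69 | 75.8% |

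If the exits discussed here fall within the planned allowance, recovering all of them gains at most 84.7 − 80.7 = 4.0 percentage points. If five per arm come on top of it (an assumption), the cost is 80.7 − 75.8 = 4.9 points.

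The SD is that of a 6-month registry score, whereas the primary analysis concerns improvement at 12 months. These powers inherit that substitution from the plan.

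**3. Possible shift in the estimate.** If a fraction p of one arm is dropped and those patients would have improved D points less than the rest, the mean of the remaining patients exceeds the full-arm mean by p × D. All values of p and D are assumptions.
- 3 of 50 dropped, D = 8 (about 1 SD): 0.06 × 8 = 0.48 point, about one tenth of the 5-point target (0.48 / 5 = 0.096).
- 5 of 50 dropped, D from 5 to 8.3: 0.10 × 5 = 0.50 to 0.10 × 8.3 = 0.83 point.
- The same losses with the same deficit in both arms: the shifts cancel in the difference (0.48 − 0.48 = 0).

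**4. Does the Investigator know the arm?** Section 17.2 does not say. The inference rests on four places: section 7.0 has the Principal Investigator record the allocation; section 13.0 makes Investigators orthopaedic surgeons; the one Principal Investigator and six co-Investigators of section 1.0 match the approximately 7 operating surgeons of section 7.0; and section 9.0 describes visibly different instruments in the two arms.

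**5. Does anything else recover the score?** Sections 16.0 and 21.2 promise attempts to complete missing data, but name no method and do not mention patients recorded as no longer participating. No section provides for postal or telephone completion, and none forbids it.

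**The case against.** The strongest reply is that the list in section 17.2 records dispositions and does not order anyone's removal. It includes completion, death, loss to follow-up and an open category, and it feeds the Study Completion Form. Missing a visit is also not the same as leaving: section 1.0 treats it as a missed visit, and section 6.3 admits to the extension patients who completed either the 6-month or the 12-month visit. This reading is fair, and it limits the point to scores that may be lost. A reader might infer that they will be lost. The documents do not say so, since sections 16.0 and 21.2 offer general retrieval and section 12.2 does not state who is excluded.

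A reader might also infer that section 17.2 contradicts section 17.1. It does not. The statement in 17.1 that participants are not restricted concerns concurrent procedures and medications. A patient can be free to receive other treatment and still become too ill to continue.

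Nor does the text give an unblinded Investigator open discretion. Withdrawal requires that the patient be unable to continue and that the cause be unrelated to the study. What stands is that neither condition has criteria, and that being unable to continue is not separated from being unable to attend.

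Finally, some illness prevents self-completion, some unwillingness to return is a refusal that must be respected, and unrelated illness should be roughly balanced between arms by randomisation. All of this is right. It reduces the number of recoverable scores and the likely bias, but it does not supply the missing instruction.

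**Conclusion.** The point holds as an avoidable weakness in follow-up. Section 17.2 merges the end of clinic attendance with the end of outcome collection, and no section provides a route for obtaining a self-completed score remotely or after exit. Some obtainable 12-month scores may be lost, possibly informatively.

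The size cannot be determined, because the documents give no exit rates by reason. On the assumptions shown it is modest: about 4 to 5 percentage points of power for every five patients per arm, and about half a point of shift in a deliberately one-sided case. That remote completion is feasible is inferred from the instrument being self-completed; the protocol does not state it. That the withdrawing Investigator knows the arm is likewise an inference, mainly from section 7.0. The change is worth making because it is cheap and protects the primary outcome.

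**What to change.** State in section 17.2 that concurrent illness, inability or unwillingness to attend, and Investigator withdrawal for an unrelated condition end clinic attendance only. Unless the patient withdraws consent to data collection or cannot complete the form, seek the 12-month Oxford Knee Score by post or telephone within the 12-month window, together with the other self-completed scores, and keep the patient in the primary analysis in the arm to which he or she was randomised. Have the Study Completion Form record separately whether visits have stopped and whether consent to data collection has been withdrawn.

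The cost is protocol wording, which needs Ethics Committee approval under section 18.0, and a few posted forms or calls by existing staff. The downside is that a few scores come by a different mode, so the mode should be recorded. The graphic pain scale would need the posted form, and the examination items of the International Knee Society Score would still be missing for patients who do not attend.

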17.3 Emergency Unblinding

In the case of an Adverse Event, a participant may require un-blinding of treatment allocation (E.g. if revision surgery is required, or total knee replacement required on the opposing limb). In such case, deemed appropriate by the Principal Investigator, the participant may be notified of their allocation by the Principal Investigator, or designee and immediate notification should be sent to the study Sponsor, including the date un-blinding occurred. If a patient is un-blinded they will be terminated from the study.

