12.2 Data Capture and Analysis

All data will be recorded on 2-part NCR paper Case Report Forms (CRFs). The surgeon will complete and sign forms at the time of completion. Original CRFs will be collected by Stryker for data entry. Copies will remain at the Investigator site. Archiving will be undertaken in accordance with ICH/GCP guidelines (Appendix 6).

Any unclear or ambiguous data will be queried and all cleaned data will be entered into a database for tracking purposes.

The primary outcome data gathered from patients in each study group will be pooled and summarized.

For the primary objective of the study, the 95% confidence interval of the difference in total Oxford Knee Score improvement (at 12 months post-operative) between the Intervention Group and the Control Group will be computed. Two and five year data will be analysed as per the 12 month data.

For secondary objectives, independent two-sample t-test or Wilcoxon non-parametric rank-sum test will be used to compare the International Knee Society Score (IKSS), Forgotten Joint Score (FJS), WOMAC, EQ-5D and VAS Pain scores between the Intervention Group and the Control Group at all available visits. Please note that the test we intend on using will be dependent on the distribution of the data collected following appropriate normality testing. Adjustments will be made for multiple testing at each level.

Independent two-sample t-test or Wilcoxon non-parametric rank-sum test will also be used to compare cost-effectiveness and cost-utility between the Intervention Group and the Control Group. As mentioned above, this will also be dependent on the distribution of the data collected.

Adverse events will be tabulated separately and reviewed for any commonalities. Revision surgery data from the Extension Study will be compared to the revision rates reported in the National Joint Registry report at 2 years and 5 years. A cost benefit analysis will be undertaken with the use of data from the Australian Government Hospital Casemix Protocol Annual Report.

A formal interim analysis will take place following completion of the ShapeNZRCT-10 study (12 month visit). Additionally, formal interim analyses will take place following all participants' completion of the 2 year visit and again following completion of all participants' 5 year follow-up visits.

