19.2 Reporting of Events

Adverse Events:

Any adverse event that occurs at any time point from the beginning of the surgical procedure until either the patient is terminated from the study, or 30 days post-completion, should be recorded as follows:

All information on general medical, operative and device related complications (adverse events) will be documented on Case Report Forms (CRFs). Information should include date of occurrence, description, severity, relationship to study device, treatment and date of resolution.

The Investigator must determine if the event is related to the device. Any adverse event in a study patient must be monitored until the event is resolved or considered non-clinically significant by the Investigator.

Expected Events: Should be reported to the Sponsor soon as possible, but not later than ten working days after the Investigator first learns of the effect.

Adverse Device Events

Should any adverse device events occur, the study staff will ensure that these are documented by the Investigator and reported immediately to the Sponsor. They should also be reported to the reviewing Ethics Committee and Institution as soon as possible, but not later than fifteen working days after the Investigator first learns of the effect, unless an earlier timeline is specified by individual study sites. The Investigator with the Sponsor will conduct an evaluation of such effects. Following this evaluation, if the Investigator determines that an unanticipated adverse device effect presents an unreasonable risk to participants, the Investigation will be terminated as soon as possible. Termination shall occur no later than five working days after the Investigator makes this determination and no later than fifteen working days after the Investigator first receives notice of the unanticipated adverse effect.

Serious Adverse Events:

Any adverse event that is considered to be of serious nature and occurs at any time point from the signing of Informed Consent Form until either the patient is terminated from the study, or 30 days post-completion, should be recorded as follows:

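### Sections 17.2 and 17.3 end participation after study-knee re-operation or actual un-blinding, with no provision for collecting the 12-month Oxford Knee Score and no analysis rule in 12.2; the likely bias is small and the fix cheap

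*Combined protocol and SAP*

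**What the plan says.** **Ending participation.** Section 17.2 lists, among the circumstances in which a patient does not continue, "Re-operation of the affected knee joint, including revision of total knee replacement components". Section 17.3 allows the Principal Investigator to reveal the allocation after an adverse event, for example "if revision surgery is required, or total knee replacement required on the opposing limb". Revealing it is discretionary; the consequence is not: "If a patient is un-blinded they will be terminated from the study".

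**Adverse events.** Section 19.2 records new events "until either the patient is terminated from the study, or 30 days post-completion". The triggering event is still followed: "Any adverse event in a study patient must be monitored until the event is resolved or considered non-clinically significant by the Investigator".

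**Primary analysis.** Section 12.2 specifies "the 95% confidence interval of the difference in total Oxford Knee Score improvement (at 12 months post-operative"), between the two groups. It names no analysis set, no handling of missing scores and no rule for re-operated or un-blinded patients. The visit windows in Section 1.0 put the 12-month visit between months 10 and 14.

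**Extension.** Section 3.0 makes revision and re-operation rates a secondary objective of the extension. Section 6.3 admits patients who completed the 6-month or the 12-month visit. Section 6.4 bars revised patients. Section 5.0 places the invitation after the 12-month visit. Under Section 12.2, "Revision surgery data from the Extension Study will be compared to the revision rates reported in the National Joint Registry report", and "Adverse events will be tabulated separately and reviewed for any commonalities".

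**The concern.** Re-operation and un-blinding happen after randomisation, and re-operation may depend on the alignment method, which is what the trial compares. If the affected patients drop out of the 12-month comparison, the two sets that remain are no longer those that randomisation produced. Suppose more ShapeMatch patients are terminated and they do worse than average. The retained ShapeMatch mean is then too high, which favours both a claim of comparable improvement (the primary objective in Section 3.0) and a claim of superiority (the hypothesis in the same section). The direction reverses if more Navigation patients are terminated. A score that was never collected cannot be recovered at analysis.

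The same rules also work against the extension's aim of determining revision and re-operation rates.

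**Working it through.** **1. The plan's own figures.** Inputs from Section 12.1: difference 5 points (37 to 42), SD 8.30, power 80%, significance level 5% (taken as two-sided).
- Normal approximation: 2 × (1.960 + 0.842)² × 8.30² / 5² = 43.3, so 44 per group. The t-test version gives 44.24, so 45, as stated.
- Allowance: 45 / (1 − 0.10) = 50, as stated.

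These figures are not in dispute. The 5 extra patients per group replace numbers; they do not supply the outcomes of particular patients who leave because of an event.

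**2. Is the 12-month score lost?** No sentence says so outright. It follows from the end of participation together with the absence of any provision for later collection. Sections 16.0 and 21.2 say that incomplete data will be sought, which is a general data-quality statement and not an analysis rule. An event after the 12-month visit does not touch the primary endpoint.

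**3. Size of the shift.** Assumed, because the documents give no event rates, no OKS after such events and no SD of improvement:
- 50 per arm, with similar pre-operative scores;
- SD 8.30, which is the registry's 6-month raw score;
- terminated patients score g points below the all-randomised mean of their own arm, with g = 5 or 10.

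With k of 50 terminated, the retained mean exceeds the arm's mean by k·g/(50 − k). The shift in the between-group difference is

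k₁·g/(50 − k₁) − k₀·g/(50 − k₀).

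| Terminated | g = 5 | g = 10 |
|---|---|---|
| equal counts | 0 | 0 |
| 1 vs 0 | 5/49 = 0.10 | 10/49 = 0.20 |
| 2 vs 1 | 10/48 − 5/49 = 0.11 | 20/48 − 10/49 = 0.21 |
| 3 vs 0 | 15/47 = 0.32 | 30/47 = 0.64 |
| 5 vs 1 | 25/45 − 5/49 = 0.45 | 50/45 − 10/49 = 0.91 |

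If g differs by arm, equal counts also give a shift. If g is near 0, as it may be for opposite-limb replacement, there is none.

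**4. Scale.** The 95% CI half-width is t × 8.30 × √(1/n₁ + 1/n₀). For 50 vs 50 it is 1.98 × 1.66 = 3.29; for 45 vs 49 it is 1.99 × 1.714 = 3.40.

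**5. False-positive rate.** If the all-randomised means are exactly equal, the shift is a false difference. From the noncentral t distribution, the two-sided error moves from 5.0% to the following:
- g = 5: 5.0% (1 vs 0), 5.4% (3 vs 0), 5.8% (5 vs 1);
- g = 10: 5.2%, 6.6%, 8.2% for the same counts, and 5.2% for 2 vs 1.

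If instead the retained patients are truly equal, the same shift is a missed deficit and there are no excess false positives.

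**6. Power.** For 5 points (t-test), power is 80.7% at 45 per group and 78.9% at 43, so it changes little.

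**7. Extension, provisions side by side.**
- *Re-entry.* Section 6.3 would admit an unrevised patient terminated after the 6-month visit. Section 5.0 ties the invitation to the 12-month visit, which that patient does not attend. Whether such patients can re-enter is unclear.
- *Interim events.* The medical history review in Section 11.0 recovers events only from the end of the 12-month period. Events between, say, a month-7 termination and month 12 fall outside it.
- *During the extension.* Nothing limits Sections 17.2 and 17.3 to the first year. After a re-operation or an un-blinding in the extension, a later revision can go unrecorded.
- *Registry comparison.* A revision before extension enrolment is recorded as an adverse event. Section 6.4 then bars the patient, and Section 12.2, read literally, compares only extension revisions with the registry.

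**The case against.** **Section 17.2 may be only a list of disposition reasons.** It mixes study completion, inability to return, concurrent illness and other reasons, and leads to a Study Completion Form. Section 17.1 also says that patients needing concurrent procedures are not restricted. This stands as a possible reading; only 17.3 is plainly mandatory. But no section says that follow-up continues after a re-operation, so the gap remains.

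**Section 17.3 has a reason.** The OKS is patient-completed (Section 11.0), and Section 7.0 blinds patients to limit bias in the questionnaires. A score after revision may also no longer reflect the allocated alignment. This stands as a real trade-off. It does not explain dropping re-operated patients who are still blinded, and it is no reason not to collect the score.

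**The size is assumed throughout and probably small.** This stands. At 2 vs 1 terminated and a 10-point gap, the shift is 0.21 points.

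**Stronger readings that the documents do not support.** A reader might infer that everyone needing a revision or an opposite-limb replacement is terminated under 17.3; only actual un-blinding triggers it. A reader might infer that revisions vanish from the safety data; the triggering event is recorded and monitored, and Section 12.2 tabulates adverse events. A reader might also assume a larger gap (17 points with 5 vs 1 gives 85/45 − 17/49 = 1.54 points) and call the primary result unreliable. Nothing in the documents supports such a gap, or 10% vs 2% terminated before month 12.

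**Conclusion.** The point holds as a cheap improvement, not as a defect that undermines the trial. Section 17.3 requires termination after actual un-blinding, 17.2 lists study-knee re-operation as a reason for not continuing, and neither these sections nor 12.2 says how the 12-month OKS is to be obtained or analysed afterwards. Bias needs a difference between arms in the rates or outcomes of terminated patients; with both equal there is none. Under assumed gaps of 5 to 10 points and 1 vs 0 to 5 vs 1 terminated, the shift is 0.1 to 0.9 OKS points, well inside the confidence interval half-width.

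The mismatch between these rules and the extension's revision and re-operation objective needs no assumed rate: the sections should be reconciled whatever the event counts turn out to be.

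**What to change.** **Sections 17.2 and 17.3.** Separate re-operation and un-blinding from the end of study follow-up. Unless consent is withdrawn, record the event and its date, and keep collecting the scheduled questionnaires and adverse events.

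**Section 12.2.** Analyse all randomised patients in their allocated group whatever these events. For scores still missing, use a likelihood-based repeated-measures model on the scheduled OKS visits (pre-operative, 6 weeks, 6 and 12 months) and state its missing-at-random assumption. Add a sensitivity analysis without post-un-blinding scores. It shows how far the result depends on them; it need not bracket the bias, since the two analyses carry different biases and may both lie on the same side of the truth.

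**Extension.** Reconcile 17.2, 17.3 and 6.4 with the revision and re-operation objective. Count revisions from the date of surgery in all randomised patients, including those before extension enrolment. State whether a patient terminated before month 12 may be invited, and from what date interim events are recovered.

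**Cost.** A protocol amendment with written Ethics Committee approval (Section 18.0), and probably revised participant information. Data collection uses visits already scheduled. The downside is that a few patients will answer questionnaires un-blinded, which the blinding in Section 7.0 was meant to avoid.
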